ICF	Informed Consent Form
ICH	International Conference on Harmonization
ICMJE	International Committee of Medical Journal Editors
IEC	Independent Ethics Committee
IFN	Interferon
IFNR	Interferon Receptor
Ig	Immunogenicity
IgA	Immunoglobulin A
IgG	Immunoglobulin G
IgG1	Immunoglobulin G1
IgM	Immunoglobulin M
IN	Investigator Notification
INR	International Normalized Ratio
IRB	Institutional Review Board
IUD	Intrauterine Device
IUS	Intrauterine System
i.v.	Intravenous(ly)
IWCLL	International Working Group - CLL
JAGS	Just Another Gibbs Sampler
LC-MS/	Liquid Chromatography Mass Spectrometry Assays
LDH	Lactate Dehydrogenase
LFT	Liver Function Test
LLOQ	Lower Limit Of Quantification
mAb	Monoclonal antibody
MAP	Meta-Analytic-Predictive
MCH	Mean Corpuscular Hemoglobin
MCL	Mantle Cell Lymphoma
MCMC	Markov Chain Monte Carlo
MCV	Mean Corpuscular Volume
MedDRA	Medical Dictionary for Regulatory Activities
MRD	Minimal Residual Disease
MRI	Magnetic Resonance Imaging
MTD	Maximum Tolerated Dose
MZL	Marginal Zone Lymphoma
NCI	National Cancer Institute

NCI CTCAE	National Cancer Institute Common Terminology Criteria for Adverse events [REDACTED]
NYHA	New York Heart Association
OCP DDI	Oncology Clinical Pharmacology Drug-Drug Interaction
ORR	Overall Response Rate
PAS	Pharmacokinetic Analysis Set
PD	Pharmacodynamics
PFS	Progression-Free Survival
PHI	Protected Health Information
PK	Pharmacokinetics
PLT	Platelets
PR	Partial Response
PR-L	PR with lymphocytosis
PT	Prothrombin Time
PTT	Partial Thromboplastin Time
PXR	Pregnane X Receptor
Q2W	Once Every Two Weeks
Q4W	Once Every Four Weeks
RA	Rheumatoid Arthritis
RD	Recommended dose
REB	Research Ethics Board [REDACTED]
SAE	Serious Adverse Event
SAP	Statistical Analysis Plan
SC	Subcutaneous
SD	Stable Disease
SDS	Sodium Dodecyl Sulfate
SLL	Small Lymphocytic Lymphoma
SUSARs	Suspected Unexpected Serious Adverse Reactions
TK	Toxicokinetic
TLS	Tumor Lysis Syndrome
TSH	Thyroid Stimulating Hormone
TPP	Time to Progression
ULN	Upper Limit of Normal
WHO	World Health Organization
WM	Waldenstrom's Macroglobulinemia

Glossary of terms

Assessment	A procedure used to generate data required by the study
Biologic Samples	A biological specimen including, for example, blood (plasma, serum), saliva, tissue, urine, stool, etc. taken from a study subject or study patient
Control drug	A study treatment used as a comparator to reduce assessment bias, preserve blinding of investigational drug, assess internal study validity, and/or evaluate comparative effects of the investigational drug
Cohort	A group of newly enrolled patients treated at a specific dose and regimen (i.e. treatment group) at the same time
Cycles	Number and timing or recommended repetitions of therapy are usually expressed as number of days (e.g.: q28 days)
Dose level	The dose of drug given to the patient (total daily or weekly etc.)
Enrollment	Point/time of patient entry into the study; the point at which informed consent must be obtained (i.e. prior to starting any of the procedures described in the protocol)
Investigational drug	The study treatment whose properties are being tested in the study; this definition is consistent with US CFR 21 Section 312.3 and is synonymous with "investigational new drug."
Investigational treatment	Drug whose properties are being tested in the study as well as their associated placebo and active treatment controls (when applicable). This also includes approved drugs used outside of their indication/approved dosage, or that are tested in a fixed combination. Investigational treatment generally does not include other study treatments administered as concomitant background therapy required or allowed by the protocol when used in within approved indication/dosage
Medication number	A unique identifier on the label of each study treatment package which is linked to one of the treatment groups of a study
Other study treatment	Any drug administered to the patient as part of the required study procedures that was not included in the investigational treatment
Patient Number	A unique identifying number assigned to each patient/subject/healthy volunteer who enrolls in the study
Personal Data	Subject information collected by the Investigator that is transferred to Novartis for the purpose of the clinical trial. This data includes subject identifier information, study information and biological samples.
Randomization number	A unique treatment identification code assigned to each randomized patient, corresponding to a specific treatment arm assignment
Stage related to study timeline	A major subdivision of the study timeline; begins and ends with major study milestones such as enrollment, randomization, completion of treatment, etc.
Study treatment	Includes any drug or combination of drugs in any study arm administered to the patient (subject) as part of the required study procedures, including placebo and active drug run-ins. In specific examples, it is important to judge investigational treatment component relationship relative to a study treatment combination; study treatment in this case refers to the investigational and non-investigational treatments in combination.
Study treatment discontinuation	Point/time when patient permanently stops taking study treatment for any reason
Treatment group	A treatment group defines the dose and regimen or the combination, and may consist of 1 or more cohorts. Cohorts are not expanded, new cohorts are enrolled.

Variable	Identifier used in the data analysis; derived directly or indirectly from data collected using specified assessments at specified time points
Withdrawal of study consent	Withdrawal of consent from the study occurs only when a subject does not want to participate in the study any longer, and does not allow any further collection of personal data.

Amendment 06 (20-Oct-2021)

Amendment rationale

The purpose of this amendment is primarily three fold:

[REDACTED] 3) allow for the closure of Arm B (patients with BTK inhibitor resistance mutations) due to slower than anticipated enrollment.

[REDACTED]

[REDACTED]

- 3) The decision to close Arm B is not based on any safety concerns. Patients currently enrolled may continue on study as long as they are tolerating study treatment and will continue to be followed per protocol.

Other changes that have been incorporated into the amendment are as follows:

- Update Exclusion Criteria # 3 to modify the washout period (from 30 days to 2 weeks or 5 half-lives, whichever is shorter) for drugs used in combination with ibrutinib as first line treatment or as a sequential combination partner. For subjects that received antibodies, the washout period is 4 weeks prior to study treatment. This will allow patients who are in need of urgent therapy for leukemia control to commence the study treatment as soon as possible.

3. Update the guidelines for determination of MTD to the most current standard. The change in the guidance language was necessary to clarify that listed conditions only apply to MTD declaration, as RDE has already been assessed.
4. [REDACTED]
5. Correct minor inconsistencies and typographical errors throughout the document.

Study status

At the time of this amendment, dose escalation is ongoing and a total of 15 patients have been enrolled.

Changes to the protocol

Changes to specific sections of the protocol are shown in the track change version of the

[REDACTED]

IRBs/IECs

A copy of this amended protocol will be sent to the Institutional Review Board (IRBs)/Independent Ethics Committee (IECs) and Health Authorities.

The changes described in this amended protocol require IRB/IEC approval prior to implementation.

The changes herein affect the Informed Consent. Sites are required to update and submit for approval a revised Informed Consent that takes into account the changes described in this protocol amendment.

[REDACTED]

Amendment 04 (November 2019)

Amendment rationale

The purpose of this amendment is to address the following health authority requests:

- Clarify that treatment decisions will be solely made based on radiological and clinical response following IWCLL response criteria.
- Revise the study protocol to state that treatment decisions will not be made based on the minimal residual disease (MRD) assessment. The statistical analysis plan will reflect this change.
[REDACTED]
- Clarify that a MRD assay implemented in the current study is multicolor flow cytometry and provide a method description of the MRD assay.
- Investigators may consider discontinuation of ibrutinib for patients who achieve a CR at the primary endpoint (C9D1) and be followed every 3 months for two years for TTP unless the patient experiences disease progression or the administration of a new therapy.
- Allow investigators to treat patients with 2 additional cycles of VAY736 therapy in combination with ibrutinib through Cycle 8 if the patient shows evidence of disease in radiological assessment or abnormal blood counts, defined by IWCLL response criteria, at the Cycle 6 Day 15 time point. Based on the preliminary efficacy data that 3 out of 5 patients had evidence of disease at the primary endpoint (C9D1), the addition of 2 more cycles of VAY736 therapy in combination with ibrutinib through Cycle 8 will help determine if further VAY736 therapy has an enhanced effect on clinical response at C9D1.
- Minor inconsistencies and typographical errors have been corrected throughout the document.

Study status

At the time of this amendment, this study has enrolled 14 patients.

Changes to the protocol

This diagram illustrates a 2D convolution operation with the following parameters:

- Input Layer:** 10 rows by 10 columns of black bars.
- Output Layer:** 10 rows by 10 columns of white bars.
- Kernel:** A 3x3 square of white bars centered in the input layer.
- Stride:** 1 (the kernel moves 1 unit at a time).
- Padding:** 1 (the input is padded with a single layer of black bars).

The output layer shows the result of the convolution, where each white bar represents the sum of the products of the kernel and the input it covers, plus a bias (not shown). The receptive field of the output layer is a 3x3 square centered on each output unit, which corresponds to the 3x3 kernel in the input layer.

IRBs/IECs

A copy of this amended protocol will be sent to the Institutional Review Board (IRBs)/Independent Ethics Committee (IECs) and Health Authorities.

The changes described in this amended protocol require IRB/IEC approval prior to implementation.

Amendment 03 (21-Aug-2019)

The primary purpose of this amendment is to:

- Expand study eligibility for dose expansion to include CLL patients who have received ibrutinib either alone or in combination as first-line CLL therapy and have either not achieved a complete response after 1 year of therapy or have developed a resistance mutation to ibrutinib at any time.

Even though ibrutinib is approved for all lines of CLL therapy, recent results from 2 phase III US Oncology cooperative group studies have demonstrated the superiority of ibrutinib or ibrutinib and rituximab combination as initial therapy in chemoimmunotherapy naive patients with improved progression-free survival and decreased toxicity compared to bendamustine and rituximab (BR) in older (≥ 65) patients and fludarabine, cyclophosphamide, and rituximab (FCR) in younger patients (< 70) (Woyach et al 2018, Shanafelt et al 2018). There was an overall survival advantage with ibrutinib and rituximab in younger patients (Shanafelt et al 2018). These studies have definitively set ibrutinib or ibrutinib and rituximab as the standard first-line therapy in all patients with CLL without contraindications. Despite its remarkable clinical activity, the limitations of ibrutinib therapy include intolerance in a subset of patients who experience adverse events, emergence of resistance mutations, and absence of deep complete remissions which necessitates indefinite continuous therapy (Byrd et al 2014, O'Brien et al 2018). Indefinite therapy with extended dosing for years is a major limitation of ibrutinib, as it puts patients at risk for chronic toxicities, such as hypertension, atrial fibrillation, and cardiovascular events (Wiczer et al 2017). In addition, the cost of ibrutinib is substantial and indefinite ibrutinib treatment will be costly for both patients and the healthcare system as a whole (Shanafelt et al 2015). As ibrutinib is now the standard frontline therapy for CLL, these issues will affect a growing number of people.

In the current study, the addition of 6 cycles of [REDACTED], antibody VAY736 (12 doses) to ibrutinib for patients who are receiving ibrutinib after progression on a prior line of therapy and have either not achieved a complete response (CR) or have developed a resistance mutation has now been shown to be safe. Eleven patients have been treated at 3 dose levels and demonstrated improved clinical activity with 1 patient achieving a minimal residual disease (MRD) negative CR and one patient achieving a MRD positive CR at 9 months (time of the final response) at the initial dose level. The other 3 patients to reach the 9-month assessment had stable disease. The study treatment has been shown to be safe, without dose limiting toxicities (DLTs). Five of eleven patients experienced adverse events related to study treatment. The most common adverse events related to study drug have been constipation (G1), hypertriglyceridemia (G1), abdominal distension (G2), blood alkaline phosphatase increased (G1), diarrhea (G2) and an infusion-related reaction (G2).

- Recommend that investigators consider discontinuation of ibrutinib for patients who achieve [REDACTED]. This will allow investigators to follow patients for durability of response and minimize intolerance and toxicities associated with continuous ibrutinib therapy while maximizing patient quality of life. Patients will discontinue all therapy and be observed off therapy for progression.

[REDACTED]

- Allow investigators to treat patients with 2 additional cycles of VAY736 therapy in combination with ibrutinib through Cycle 8 if the patient does not achieve a [REDACTED] status in the blood at the Cycle 6 Day 15 time point. Based on the preliminary efficacy data and MRD positivity seen in 4 out of 5 patients that have reached the primary endpoint (C9D1), the addition of 2 more cycles of VAY736 therapy in combination with ibrutinib through Cycle 8 will help determine if prolonged VAY736 therapy has an effect on [REDACTED]
[REDACTED]
- [REDACTED]
- [REDACTED]
- [REDACTED]
- Minor inconsistencies and typographical errors have been corrected throughout the document.

Study Status

- At the time of this amendment, dose escalation is ongoing and a total of 11 patients have been enrolled.

Changes to the Protocol

Term	Percentage
Climate change	100
Global warming	98
Green energy	95
Carbon footprint	92
Sustainable development	88
Renewable energy	85
Emissions reduction	82
Green economy	78
Carbon tax	95

[REDACTED]

[REDACTED]

[REDACTED]

[REDACTED]

[REDACTED]

[REDACTED]

[REDACTED]

[REDACTED]

[REDACTED]

IRBs/IECs

A copy of this amended protocol will be sent to the Institutional Review Board (IRBs)/Independent Ethics Committee (IECs) and Health Authorities.

The changes described in this amended protocol require IRB/IEC approval prior to implementation.

The changes herein affect the Informed Consent. Sites are required to update and submit for approval a revised Informed Consent that takes into account the changes described in this protocol amendment.

[REDACTED]

Amendment 02 (03-Dec-2018)

Amendment rationale

The purpose of this amendment is to address the following changes:

- Clarify that subjects enrolled in the study may receive either ibrutinib tablets or capsules as these formulations are bioequivalent.
- [REDACTED]
- [REDACTED]
- [REDACTED]
- Update Table 14-11 in Appendix 3 based on the Novartis PK Sciences DDI List (v01 released in 2018 January).
- Provide other minor changes/corrections for consistency and/or clarification.

Study status

At the time of this amendment, dose escalation is ongoing and 7 patients have been enrolled.

Changes to the protocol

[figure not shown]
Term	Percentage
GMOs	10%
Organic	20%
Natural	30%
Artificial	40%

IRBs/IECs

A copy of this amended protocol will be sent to the Institutional Review Board (IRBs)/Independent Ethics Committee (IECs) and Health Authorities.

The changes described in this amended protocol require IRB/IEC approval prior to implementation.

Amendment 01 (02-Nov-2017)

Amendment rationale

The purpose of this amendment is to address the following health authority requests:

- Clarify that patients will not be enrolled based on lack of MRD (-) CR after > 1 year of treatment with ibrutinib
- Revise the study protocol to only enroll patients with CLL in both the dose escalation and expansion parts who are receiving ibrutinib in the relapsed setting
- Revise the dose limiting toxicity (DLT) definitions to remove previously listed exceptions
- Add direct and indirect Coomb's testing at baseline and as clinically indicated

Study status

At the time of this amendment, this study has not been opened for recruitment.

Changes to the protocol

[REDACTED]

IRBs/IECs

A copy of this amended protocol will be sent to the Institutional Review Board (IRBs)/Independent Ethics Committee (IECs) and Health Authorities.

The changes described in this amended protocol require IRB/IEC approval prior to implementation.

[REDACTED]

Protocol summary:

Title	Phase Ib open-label study of VAY736 and ibrutinib in patients with chronic lymphocytic leukemia (CLL) on ibrutinib therapy
Brief title	Phase Ib study of VAY736 and ibrutinib in patients with CLL
Sponsor and Clinical Phase	Novartis Phase Ib
Investigation type	Drug, Biological
Study type	Interventional
Purpose and rationale	The purpose of this study is to characterize the safety, tolerability, pharmacokinetics (PK), pharmacodynamics (PD), and antitumor activity of the combination of VAY736 with ibrutinib.
Primary Objective(s) and Key Secondary Objective	To determine the maximum tolerated dose (MTD) and/or RD (recommended dose) of the combination of VAY736 and ibrutinib. To characterize the safety and tolerability of the combination of VAY736 and ibrutinib
Secondary Objectives	To assess any preliminary antitumor activity of the combination of VAY736 and ibrutinib To characterize the PK of VAY736 and ibrutinib when used in combination therapy To assess the immunogenicity (IG) following one or more intravenous infusions of VAY736
Study design	This is a Phase Ib, open-label study to characterize the safety, tolerability, PK, PD, and preliminary anti-tumor activity of the combination of VAY736 with ibrutinib in patients with CLL who have been receiving ibrutinib for more than one year and who have not achieved a complete response to ibrutinib or who have developed a resistance mutation to ibrutinib. The study has two parts, dose escalation and dose expansion. The dose escalation part will determine the maximum tolerated dose (MTD) or the recommended dose (RD) for expansion of the combination of VAY736 with ibrutinib. In the expansion part, patients will be enrolled to one of two arms to further explore the safety, tolerability, and preliminary efficacy of the combination. As of Amendment 6, patients will no longer be enrolled into Arm B (expansion).
Population	Adults with CLL who have been receiving ibrutinib following relapse on another approved therapy and either have not had a complete response after 1 year of treatment or have developed a resistance mutation to ibrutinib without clinical relapse at any time during treatment. The dose expansion part of the study will also include patients who have received ibrutinib either alone or in combination (or have received ibrutinib continuously with multiple sequential combination partners) as first-line therapy and have either failed to achieve a complete response after 1 year of therapy or have developed a resistance mutation to ibrutinib.
Inclusion criteria	Written informed consent Ibrutinib dose Escalation: Patients must be receiving 420 mg ibrutinib Expansion: Patients may be on a dose of ibrutinib lower than 420 mg. Any dose must have been stable for 2 months prior to the start of study treatment. Diagnosis of CLL as per World Health Organization (WHO) classification Lack of a complete response after receiving ibrutinib for > 1 year OR presence of known ibrutinib resistance mutation Platelets $\geq 25 \times 10^9/L$ without transfusion support within 7 days of the first dose of VAY736 Eastern Cooperative Oncology Group (ECOG) performance status of 0-2

Exclusion criteria	Receipt of live vaccine within 4 weeks of starting VAY736 Known history of HIV Active hepatitis B or C infection
Investigational and reference therapy	VAY736 Ibrutinib
Efficacy assessments	Rate of patients with CR (complete response) as assessed by investigators per IWCLL at cycle 9 day 1 Overall response rate (ORR) assessed by investigators per IWCLL criteria and Time To Progression (TTP) Clearance of ibrutinib resistance mutations (BTKC481 and/or PLCy2 hotspot), defined as less than 1% mutation bearing alleles (Arm B only). [REDACTED]
Safety assessments	Safety Escalation only: Incidence of DLTs in cycle 1 (28 days) Escalation and expansion: Incidence and severity of AEs and SAEs, including changes in laboratory parameters and vital signs Tolerability Dose interruptions, reductions, and dose intensity
Other assessments	Plasma concentrations of VAY736 and ibrutinib and derived parameters Presence of anti-VAY736 antibodies [REDACTED] [REDACTED] [REDACTED]
Data analysis	The study data will be analyzed and reported based on patient's data from the dose escalation and dose expansion parts of the study up to the time when all patients have completed the treatment period and follow-up for disease progression or discontinued the study for any reason. Data will be summarized using descriptive statistics (continuous data) and/or contingency tables (categorical data) for demographic and baseline characteristics, efficacy measurements, safety measurements, and all relevant PK and PD measures. The Bayesian logistic regression model with overdose control will be used to assess safety for new patients treated at the dose levels that will be used for dose cohorts that occur after the initial dose cohort.
Key words	Chronic lymphocytic leukemia, CLL, VAY736, ibrutinib, [REDACTED] [REDACTED], ibrutinib resistance mutation, BTK (Bruton's tyrosine kinase), Phase Ib

1 Background

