5.2 Inclusion criteria

Patients eligible for inclusion in this study have to meet **all** of the following criteria:

Patient must meet the following laboratory values at the screening visit unless cytopenias are related to CLL:

1. Diagnosis of chronic lymphocytic leukemia (CLL) meeting criteria established in the World Health Organization (WHO) classification of hematologic disorders or International Workshop on Chronic Lymphocytic Leukemia (IWCLL) ([Hallek et al 2018](#)). Variant immunophenotype and prolymphocytic morphology change after diagnosis of CLL is allowed.
2. Age \geq 18 years
3. [REDACTED]
4. Male patients agree to avoid fathering a child as per the ibrutinib package insert

5. Dose escalation:
 - a. On ibrutinib > 1 year following relapse from another approved therapy without achieving a complete response

[figure not shown]
OR
 - b. On ibrutinib following relapse with another approved therapy and the presence of a known ibrutinib resistance mutation (BTK or PLC γ 2) at ≥ 1 variant allele frequency OR $< 1\%$ with two separate measurements at least 4 weeks apart with increasing variant allele frequency.
6. Dose expansion:
 - a. Arm A: On ibrutinib > 1 year following relapse from another approved therapy without achieving a complete response and patients who have received ibrutinib either alone or in combination (or have received ibrutinib continuously with multiple sequential combination partners) as first-line therapy and have failed to achieve a complete response after 1 year.
 - b. Arm B: On ibrutinib following relapse with another approved therapy and patients who have received ibrutinib either alone or in combination (or have received ibrutinib continuously with multiple sequential combination partners) as first-line therapy and the presence of a known ibrutinib resistance mutation at $\geq 1\%$ variant allele frequency OR $< 1\%$ with two separate measurements at least 4 weeks apart with increasing variant allele frequency. *Note: As of Amendment 6, patients will no longer be enrolled into Arm B.
7. Ibrutinib dose:
 - Escalation: Patients must be receiving 420 mg ibrutinib
 - Expansion: Patients may be on a dose of ibrutinib lower than 420 mg. Any dose must have been stable for 2 months prior to the start of study treatment.
8. Absolute Neutrophil Count ≥ 750 cells/ μ L ($0.75 \times 10^9/L$) independent of growth factor support within 7 days of the first dose of VAY736

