7.2.2.7 Ibrutinib resistance mutation

Blood or bone marrow samples collected on the days outlined in [Table 7-1](#) or [Table 7-2](#) will be analyzed in accordance with the CVAY736Y2102 laboratory manual.

7.2.3 Pharmacokinetics and immunogenicity:

PK samples will be collected from all enrolled patients to assess PK properties of VAY736 and ibrutinib. Immunogenicity (IG) samples will also be collected to monitor appearance of anti-drug antibodies (ADAs) directed against VAY736. Refer to [Table 7-6](#), [Table 7-7](#) and [Table 7-8](#) for details on PK and IG sample collections.

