10.5.2 Other secondary efficacy objectives

All efficacy analyses are based on FAS.

Rate of CR at C9 for expansion arm A and arm B: The proportion of patients with CR, assessed by investigators per IWCLL criteria (see [Appendix 1](#) for details) at C9 will be provided. The rate of CR at C9 is the primary endpoint for the evaluation of anti-tumor activity and will be analyzed for each expansion arm using a Bayesian modeling approach.

A minimally informative beta distribution is used as prior distribution with parameters $a=0.25$ and $b=1$. This assumes *a priori* response rate of 20%.

Posterior summaries for CR rate (posterior mean, including 90% credible intervals and the posterior probability that the true CR rate falls in the activity intervals defined below) will be provided:

Posterior probability of response rate intervals:

- [0, 20%) – clinically not meaningful
- [20%, 40%) – moderate clinical benefit
- [40%, 100%) – superior clinical benefit

In addition, exact confidence interval (90% CI) also will be provided.

Clearance of ibrutinib resistance mutation for expansion arm B is defined as less than 1% mutation bearing alleles (BTKC481 and/or PLC γ 2) during treatment. The proportion of patients with negative mutation will be provided along with corresponding 90% exact confidence interval (CI).

Overall response rate (ORR) is defined as best overall response (BOR) of complete response (CR) or partial response (PR), assessed by investigators per IWCLL criteria (see [Appendix 1](#) for details). ORR for each expansion arm along with corresponding 90% exact confidence interval (CI) will be provided.

Time to progression (TTP) is the time from start of treatment to the date of event which is defined as the first documented progression or death due to underlying cancer. If a patient has not had an event, time to progression is censored at the date of last adequate disease assessment.

TTP will be described using Kaplan-Meier methods and appropriate summary statistics. .

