2.8 Analysis of other secondary objective(s)

2.8.1 Efficacy analysis

Evaluation of anti-tumor activity will be based on investigators' assessment per IWCLL criteria (see VAY736Y2102-CSP-Appendix 1 for details) as documented in the eCRF. The variables used to evaluate anti-tumor activity are CR/CRi rate, clearance of ibrutinib resistance mutations, overall response rate (ORR), and time to progression (TTP). Analyses of these variables will use the FAS, including patients from both the escalation and expansion parts. All analyses will be provided by dose level in dose escalation and by two arms in dose expansion.

Rate of CR/CRi at C9 for expansion arm A and arm B: The proportion of patients with CR or CRi assessed by investigators per IWCLL criteria (see VAY736Y2102-CSP-Appendix 1 for details) at C9 will be provided. The rate of CR/CRi at C9 is the primary endpoint for the evaluation of anti-tumor activity and will be analyzed for each expansion arm using a Bayesian modeling approach.

A minimally informative beta distribution is used as prior distribution with parameters $a=0.25$ and $b=1$. This assumes, *a priori*, that the response rate is 20%.

Posterior summaries for CR/CRi rate (posterior mean, including 90% credible intervals and the posterior probability that the true CR/CRi rate falls in the activity intervals defined below) will be provided:

Posterior probability of response rate intervals:

- [0, 20%] – clinically not meaningful
- [20%, 40%] – moderate clinical benefit
- [40%, 100%] – superior clinical benefit

In addition, exact confidence interval (90% CI) also will be provided.

To determine which response assessments occurred at C9, response assessment dates within a window of +/- 3 days of patient's Cycle 9 visit start date or end date will be considered as C9 responses.

Clearance of ibrutinib resistance mutation for expansion arm B is defined as less than 1% mutation bearing alleles (BTKC481 and/or PCL γ 2) during treatment (up to C9). The proportion of patients with negative mutation, where negative mutation is defined as having clearance of the baseline ibrutinib resistance mutation, will be provided along with corresponding 90% exact confidence interval (CI). Note that only R665, S707, A708 and L845 variants will be considered as functional PLC γ 2 mutations. Other PLC γ 2 variants will not be considered for this analysis.

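### SAP 2.8.1 both includes and excludes escalation-part mutation carriers in the clearance analysis, and its denominator admits patients already under the 1% threshold

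*Protocol*

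**What the plan says.** **Texts that limit clearance to Arm B.** The protocol synopsis gives the endpoint as "defined as less than 1% mutation bearing alleles (Arm B only"), and protocol Table 3-1 and SAP Table 1-1 repeat the limit. Protocol 10.5.2 defines clearance for expansion Arm B. SAP 2.8.1 does the same: "Clearance of ibrutinib resistance mutation for expansion arm B is defined as less than 1% mutation bearing alleles".

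**Text that includes escalation.** The lead paragraph of SAP 2.8.1 lists four anti-tumour variables, with mutation clearance among them, and states: "Analyses of these variables will use the FAS, including patients from both the escalation and expansion parts". It then asks for all of them by dose level in escalation and by arm in expansion. The opening of protocol Section 10 gives the same general rule for efficacy.

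**Who can carry a mutation.** Escalation criterion 5b in protocol 5.2 admits patients "On ibrutinib following relapse with another approved therapy and the presence of a known ibrutinib resistance mutation" in BTK or PLCγ2. Both 5b and the Arm B criterion 6b also allow entry below 1% variant allele frequency (VAF), provided this is shown "with two separate measurements at least 4 weeks apart with increasing variant allele frequency".

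**Testing.** Protocol 7.2.2.7 ties the test to the visit tables, not to a study part or arm: "Blood or bone marrow samples collected on the days outlined in" Table 7-1 or Table 7-2.

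**Arm B.** One purpose of Amendment 06 was to "allow for the closure of Arm B (patients with BTK inhibitor resistance mutations) due to slower than anticipated enrollment". Patients already in Arm B could continue and are followed.

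**Analysis.** Protocol 10.5.2: "The proportion of patients with negative mutation will be provided along with corresponding 90% exact confidence interval (CI"). No hypothesis, alpha or power attaches to this endpoint.

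**The concern.** Two programmers working from SAP 2.8.1 could produce different clearance tables, one with Arm B alone and one with escalation carriers by dose level. The visible text of SAP Section 4, which lists the departures from the protocol, does not settle which is meant.

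The conflict would matter little if Arm B had filled to its planned 20 or so patients. It closed early, so escalation carriers, if there are any, are the only other patients in the trial who can inform this endpoint. Eliminating cells with acquired resistance is one of the aims in protocol 2.1. Protocol 1.2.4.2 also says that, once detected on ibrutinib, these mutations neither decline in frequency nor become undetectable. On that premise each observed clearance is informative without a control group.

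The denominator is a second problem, in either part. A patient admitted below 1% VAF already satisfies a definition of clearance that requires less than 1%.

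**Working it through.** **1. The plan's own figures.** The documents give no sample size or precision for clearance. The nearest figure behind the arm size is in SAP 3.1.2, the probability of seeing at least one event of 10% incidence:
- n = 20: 1 − 0.9^20 = 0.878 (stated 87.8%)
- n = 40: 1 − 0.9^40 = 0.985 (stated 98.5%)

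Both reproduce, but they concern adverse events and say nothing about clearance.

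**2. Known and unknown counts.** The Amendment 06 study status gives 15 patients enrolled in escalation (none ongoing) and 11 receiving treatment in expansion, both arms together. It gives neither the number enrolled in Arm B nor the number who entered escalation under 5b. Everything below is therefore illustrative.

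**3. Interval formula.** For x cleared of n, the 90% Clopper-Pearson limits are
- lower = Beta quantile 0.05 with parameters (x, n − x + 1)
- upper = Beta quantile 0.95 with parameters (x + 1, n − x)
- for x = 0, upper = 1 − 0.05^(1/n)

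| Cleared/n | 90% exact interval |
|---|---|
| 10/20 (planned arm size) | 0.302 to 0.698 |
| 1/3 | 0.017 to 0.865 |
| 2/5 | 0.076 to 0.811 |
| 4/10 | 0.150 to 0.696 |
| 0/3 | 0 to 0.632 |
| 0/5 | 0 to 0.451 |
| 0/10 | 0 to 0.259 |

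**4. Range of the possible gain.** Interval widths with about half cleared, for assumed Arm B sizes of 3, 5 and 11 and 0 to 8 added escalation carriers:

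| Arm B n | +0 | +3 | +5 | +8 |
|---|---|---|---|---|
| 3 | 0.848 | 0.694 | 0.614 | 0.529 |
| 5 | 0.734 | 0.614 | 0.555 | 0.489 |
| 11 | 0.529 | 0.473 | 0.443 | 0.406 |

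The planned n = 20 gives 0.396. The +0 column is a real possibility, and there the gain is nil. Only carriers at the expansion dose and schedule would enter a pooled row, so the larger additions are the less likely ones.

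**5. Effect of the sub-1% entry route.** Suppose Arm B has 5 patients. Two entered below 1% and stay there, and none of the other three clears. Counting all five gives 2/5 = 40% (7.6% to 81.1%). Counting only those with something to clear gives 0/3 = 0% (upper limit 63.2%). The 40% would be produced by the entry rule, not by treatment.

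**The case against.** A reader might infer that the plan plainly discards usable data. The documents do not support that. The lead paragraph of SAP 2.8.1 includes escalation patients, and no document shows that any escalation patient entered under 5b rather than 5a. Slow recruitment of carriers to Arm B makes a large number less plausible.

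A reader might also infer from the 11 patients that Arm B stopped well short of 20. That figure counts patients on treatment in both arms at one date, not Arm B enrollment, which is not given.

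Nor is identical testing fully shown. In the public copy the mutation row is legible in Table 7-2 (Q4W) but not in Table 7-1 (Q2W). Section 7.2.2.7 cites both tables, so the row may be lost or redacted, but sample collection under Q2W should be confirmed.

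The restriction to Arm B is also defensible as design. Protocol 2.1 gives preliminary efficacy in these specific groups to the expansion arms. Escalation spans several VAY736 doses, requires ibrutinib 420 mg and excludes the first-line ibrutinib patients allowed in expansion. This argues against merging escalation carriers into the Arm B estimate, and that part stands.

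Finally, the study is open-label, escalation had finished by Amendment 06, and the SAP already records the early-termination decision of September 2023. Widening the population now is post hoc. That also stands, and it is why the added rows need a label. None of these objections removes the contradiction or the denominator fault.

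**Conclusion.** The point holds as an inconsistency over who is analysed, together with a faulty denominator. SAP 2.8.1 gives two incompatible populations for clearance, and the visible text of Section 4 does not resolve them.

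The size of any precision gain is unknown. It runs from none, if no escalation patient entered under 5b, to a narrowing such as 8–81% to 15–70%, if five carriers at the expansion dose and schedule join an Arm B of five with 40% cleared. Even then the interval stays wide. Rows by dose level would be descriptive only: with 0 of 2 cleared the 90% upper limit is still 78%, so a dose effect on clearance could not be read from them.

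The denominator fault does not depend on escalation carriers. It applies to Arm B whenever a patient entered through the sub-1% route, and how many did is also not stated.

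This is a descriptive secondary endpoint, and no error rate or power is affected. The correction is worth making because it costs little and settles what the table will contain.

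**What to change.** In SAP 2.8.1 and Table 1-1, with an entry in Section 4:

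1. Keep expansion Arm B as the main clearance display, and say whether the FAS sentence in the lead paragraph applies to clearance.
2. Add a supplementary summary of escalation carriers by dose level, plus one pooled row for carriers treated at the expansion dose and schedule, each with its 90% exact interval. Label these as added after Arm B closure.
3. In every clearance row, including Arm B, limit the denominator to patients with a qualifying baseline mutation (BTK C481, or one of the functional PLCγ2 variants that SAP 2.8.1 lists) at VAF of at least 1%. List carriers below 1% separately.
4. State the number of carriers in each part. If escalation has none, say so and omit the extra rows.

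The cost is SAP wording, a few table rows and a post hoc label. SAP 2.3.2 already summarises baseline mutation status, so carriers can be identified. No new patients or procedures are needed, provided that escalation samples were collected as 7.2.2.7 describes. Recording the departure in SAP Section 4 leaves the protocol text as it stands.
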